1.2. Objectives

To determine whether active HD-tDCS targeting the dominant posterior TPC can improve language performance, increase language network functional connectivity, and improve abnormal patterns of resting state neuronal frequencies and synchronizations.

Specific Aim 1. Determine changes in language performance after 10 HD-tDCS stimulation sessions (QD) lasting 20 minutes at a current intensity of up to 2mA in the left TPC in a randomized, double-blind, sham-controlled, within-subject cross-over study with 20 lvPPA subjects ages 45 years and greater.

Specific Aim 2. Determine the effects of the conditions described in Specific Aim 1 on the resting state Language network-level changes in left TPC functional connectivity between the conditions described in Specific Aim 1.

Specific Aim 3. Determine the effects of the conditions described in Specific Aim 1 on the neuronal frequency distribution and connectivity measures associated with the left TPC as assessed by MEG.

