Define $\widetilde{LG}(s, g, t) \equiv Res(s, g, t)$. We will test the residuals $\widetilde{LG}(s, g, t)$ using a *three-factor crossed-nested* ANOVA, with fixed factors *group* and *time*, and random factor *subject* nested within *group*. We will test for group and time main effects, as well as the group \times time interaction. If we find significant main effects or interactions, we will perform post hoc procedures to determine which time and group combinations are significantly different.

6.4. Functional-Connectivity Changes Due to Stimulation. We will use the well established Human Connectome Project (HCP) fMRI processing pipelines implemented by [name] group at MCW, which include state-of-the-art noise removal, spatial normalization, and surface-based cortical parcellation methods.

Functional connectivity matrices will be computed by first parcellating the brain into multiple regions of interest (ROI), averaging the preprocessed fMRI signal over each ROI, and then computing the Z-transformed correlation coefficient between every ROI pair. The functional connectivity of a number of different parcellation schemes will be examined. This includes anatomical atlas based parcellation, such as the Harvard Oxford atlas, a validated probabilistic atlas implemented in FSL that divides each hemisphere into 56 regions corresponding to portions of cortical gyri and subcortical gray matter nuclei; combined anatomical and functional parcellation of regions that tend to co-activate during resting state, as implemented in Statistical Parametric Mapping (Tzourio-Mazoyer, N., et al., 2002) and purely functional delineations such as the Crad-200, a constrained spectral clustering of resting state fMRI data into 200 parcels encompassing both cortical and subcortical regions, and a high model order Independent component analysis (ICA), as advocated by HCP investigators. Targeted exploration of connectivity driven by current understanding of the pathophysiology of IvPPA will also be pursued.

We will employ age, years of education, gender, and gray matter (GM) volume as time-invariant covariates to obtain residual variables to determine LFC changes due to stimulation. We will model the LFC as a function of these nuisance regressors, using the following multiple linear regression equation, and retain the residuals as $LFC_{Res}^+(s, t)$ for further analysis:

$$LFC(s, t) = \beta_0 + \beta_1 Age(s) + \beta_2 Edu(s) + \beta_3 GM(s) + \beta_4 Gender(s) + Res(s, g, t)$$

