where $\widetilde{LFC}^+(s, g, t) \equiv Res(s, g, t)$. This regression will be performed using all of the data (i.e., all subjects, all groups, and all times). We will test the residuals $\widetilde{LFC}^+(s, g, t)$ using *three-factor crossed-nested analysis of variance* (ANOVA), with fixed factors of *group* and *time* and a random factor of *subject* nested within *group* (i.e., all subjects will be tested at all times, but the sham and stimulation groups will contain different treatment phases). We will test for both group and time main effects, as well as for the group \times time interaction. If we find significant main effects or interactions, we will perform post hoc procedures to determine which time and group (i.e., sham Vs. stimulation) combinations are significantly different.

6.5. Prediction of Changes in Correlation Between LFC and LG Before and After tDCS. A multiple linear regression is used to model LG as a linear function of LFC and test the difference in slope and intercept between the active stimulation and sham groups. If the subject is in the active stimulation group, $A(s, g) = 1$; if the subject is in the sham (placebo) group, $A(s, g) = 0$.

$$LG(s, g) = \beta_{0,0} + \beta_{0,1}A(s, g) + \beta_{1,0}LFC(s) + \beta_{1,1}LFC(s)A(s, g) + Res(s)$$

Here, **LFC(s)** represents baseline LFC for subject s (for simplicity, nuisance regressors are not shown).

6.6. Changes in Spontaneous Neuronal Oscillatory Patterns and synchronizations due to Stimulation

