Study Title: High-Definition Transcranial Direct Current Stimulation (HD-tDCS) in logopenic variant Primary Progressive Aphasia (lvPPA): Effects on Language and Neural Mechanisms.

NCT: NCT03805659

Date of document: July 06, 2023

Statistical Analysis:

- The small sample size in this study precluded group-level statistical analysis.
- Instead focused on a within subject item-level analysis.
- Language performances in each trial period were assessed separately to help control for potential carryover effects and for effects of progressive neurodegeneration.
- The Cochran's Q test was used to determine if there were any differences on a dichotomous variable across the three-trial period timepoints.
- Because the same assessment list/version was used within a given stimulation condition per participant, we coded "right" and "wrong" answers to an individual assessment item as our dichotomous variable.
- If the preliminary Cochran's Q test demonstrated a significant difference ($p<0.05$) between participant responses in a language assessment between two timepoints, a follow-up non-parametric pairwise comparison between the baseline and timepoint list was tested using a McNemar test with a false discovery rate correction (Sheppard et al., 2021; Hung et al., 2017; Tsapkini et al., 2015).
- While the Cochran's Q and post-hoc McNemar test allowed us an objective comparison between timepoints within conditions for each individual participant, we utilized a Wilcoxon-signed rank test to assess participant performance changes between aHD-tDCS and sHD-tDCS (ex: aHD-tDCS T0-T1 percentage change from baseline vs. sHD-tDCS T0-T1 percentage change from baseline). This assessment would allow us a more quantitative direct comparison between treatment conditions on an individual participant (Sheppard et al., 2021). The statistical analyses described were performed using SPSS version 27.0 (IBM, Armonk NY). A p-value of <0.05 was used to describe statistical significance.

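### Section 6.5 does not centre baseline connectivity, so its intercept test compares active with sham at zero connectivity rather than at the participants' average

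*Protocol*

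**What the plan says.** Protocol section 6.5 plans to "model LG as a linear function of LFC and test the difference in slope and intercept between the active stimulation and sham groups". In plain notation the equation is LG = b00 + b01·A + b10·LFC + b11·LFC·A + residual, with A = 1 for active and 0 for sham. The LFC term "represents baseline LFC for subject s (for simplicity, nuisance regressors are not shown").

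Section 6.2 defines LFC as connectivity between posterior temporal and inferior parietal areas on the left. Section 6.4 obtains connectivity by "computing the Z-transformed correlation coefficient between every ROI pair". It also regresses LFC on age, education, gray matter volume and gender, "using the following multiple linear regression equation, and retain the residuals as" a separately marked quantity for later use. Section 6.5 does not carry that mark.

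Section 6.6 applies the regression models used for the fMRI data to MEG connectivity, measured by coherence and two phase-lag indices. The equations are not repeated there.

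No mean, SD or range of LFC appears in either document. The SAP does not mention LFC and says the sample was too small for group-level analysis.

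**The concern.** In a model with a product term, the coefficient of A is the difference between conditions at the point where the other variable equals zero. On a Z-transformed correlation scale, zero means no correlation. It is a fixed point on the scale and need not lie near the sample mean. The equation in 6.5 is also the only one in section 6 printed with an explicit active/sham indicator, so a reader is likely to take b01 as the stimulation effect.

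The stake is how that coefficient is read. A uniform active-sham difference could be missed because b01 is estimated away from the centre of the data. A difference in slopes alone could give a b01 whose sign misleads. Section 7.8 says that effect sizes from this pilot will feed the sample-size calculation of a later trial, so a misread coefficient could be carried forward.

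**Working it through.** The plan states no figure for this test, so there is none to reproduce.

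**Inputs.** The model and the coding of A come from 6.5, and the scale of LFC from 6.4, read as Fisher's z. The design is a "within-subject cross-over study with 20 lvPPA subjects ages 45 years and greater", with two sequence groups of 10 (section 6.2). Section 6.5 gives no significance level. The SAP's is used: "A p-value of <0.05 was used to describe statistical significance". The ratio of mean to SD of baseline LFC is an assumption, taken from 0 to 4.

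**Meaning of b01.** The active-sham difference at connectivity x is b01 + b11·x. At x = 0 this is b01. At the sample mean m it is b01 + b11·m, so b01 = (difference at m) − b11·m.

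**Standard error.** Take n participants in each condition, the same LFC distribution (mean m, SD s) in both, and residual variance σ². Then:

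- Uncentred: Var(b01) = 2σ²·[1/n + m²/((n−1)s²)]
- Centred: Var(b01) = 2σ²/n
- Ratio of standard errors: sqrt(1 + (n/(n−1))·(m/s)²), close to sqrt(1 + (m/s)²)

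The crossover does not alter this ratio. If each participant's active-minus-sham difference is regressed on one baseline LFC value, the intercept variance is again proportional to 1/n + m²/((n−1)s²).

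**Results.** The power column supposes a constant active-sham difference that the centred test detects with 80% power (z = 2.8, two-sided 5%). It divides 2.8 by the large-sample factor.

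| mean/SD | SE factor, large sample | n = 20 per condition | n = 10 per group | power of uncentred test |
|---|---|---|---|---|
| 0 | 1.00 | 1.00 | 1.00 | 80% |
| 0.25 | 1.03 | 1.03 | 1.03 | 78% |
| 0.5 | 1.12 | 1.12 | 1.13 | 71% |
| 1 | 1.41 | 1.43 | 1.45 | 51% |
| 2 | 2.24 | 2.28 | 2.33 | 24% |
| 3 | 3.16 | 3.24 | 3.32 | 14% |
| 4 | 4.12 | 4.22 | 4.33 | 10% |

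For example, at mean/SD = 2, 2.8/2.24 = 1.25, and 1.25 − 1.96 = −0.71, which gives 24%. With n = 20 the standard error doubles when 1 + (20/19)(m/s)² = 4, that is at mean/SD of about 1.7.

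**Simulation check.** This used 1000 fits per setting with four nuisance covariates in the model. At mean/SD of 0.5, 1, 2 and 3 the median SE ratios were 1.13, 1.44, 2.32 and 3.31 with 20 participants in both conditions, and 1.12, 1.48, 2.38 and 3.41 with 10 against 10. The slope standard error and the joint F statistic were the same with and without centring (differences below 1e-12). With residualised LFC the intercept SE ratio to the centred model was 1.00.

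**Sign, with illustrative values.** If the difference at mean LFC 0.5 is +0.3 and the slope difference is +1.0, then b01 = 0.3 − 1.0 × 0.5 = −0.2.

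**The case against.** The strongest reply is that the plan does nothing wrong by its own terms. The title of 6.5 concerns the relation between LFC and LG. The slope difference addresses that, and centring leaves it unchanged. The plan says it will test an intercept difference, which b01 is, and it never calls b01 the average stimulation effect. Language change due to stimulation has its own analysis in 6.3. If slope and intercept are tested jointly, centring changes nothing, and the same fit can yield the active-sham difference at any LFC value. All of this stands. It confines the point to the separate intercept test and to how its result is read.

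A second reply is that 6.4 keeps LFC residuals for later use. Residuals from a fit with an intercept average zero over the data fitted, so entering them would remove most of the problem. The 6.4 fit uses all time points, so the baseline residuals alone need not average exactly zero. The wording of 6.5 points the other way: it drops the residual mark, calls the term baseline LFC, and keeps the nuisance regressors in the same model. The literal reading is unresidualised LFC, but one line from the sponsor would settle it.

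A reader might go further and infer that zero connectivity lies outside what these participants show, and hence that the standard error is much larger. The documents do not support that, because they give no LFC values. At mean/SD of 0.25 to 0.5 the inflation is only 3% to 12%. The MEG measures are a partial exception. Coherence and the phase lag index cannot be negative, so zero is their floor. This matters only if the 6.5 model is among those that 6.6 carries over, which the text allows but does not state.

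Finally, each participant receives both conditions, yet the 6.5 equation has no subject term. Centring does not repair that. It is a separate matter and leaves the SE factor above unchanged.

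**Conclusion.** The point holds in a limited form. As printed, b01 is the active-sham difference at zero baseline connectivity. Its standard error is larger than that of the centred test by a factor of 1.0 to about 4 for an assumed mean/SD of 0 to 4. Its sign can differ from the effect at the mean only when the slopes differ. This rests on three readings: LFC enters as written, the Z-transform is Fisher's, and LFC is distributed similarly in the two conditions. The mean/SD range is an assumption, and the power figures also require a difference that is constant across LFC.

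It would be wrong to infer that section 6.5 as a whole fails, or that reported results are distorted. The slope test is sound on this point, and the SAP replaces group-level analysis with item-level tests within each participant. The practical weight is therefore low: a clarification to consider, relevant if this regression is run or is taken into a later trial.

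**What to change.** In the 6.5 equation, replace LFC(s) by LFC(s) minus the mean baseline LFC, in both the main effect and the product term. Report b01 as the active-sham difference at average baseline connectivity, and keep b11 as the test of effect modification. Apply the same change to the MEG models if 6.5 carries over to them. If the 6.4 residuals were intended, say so and use their notation.

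The cost is one line of analysis text. Model fit, the slope test and any joint test are unchanged, and no further data are needed.

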1. STUDY OBJECTIVES

The logopenic variant of Primary Progressive Aphasia (lvPPA) is an untreatable neurodegenerative disorder that is often referred to as the 'language form' of Alzheimer's Disease (AD). Transcranial Direct Current Stimulation (tDCS) has emerged as a safe and potentially effective tool that appears to enhance language production when delivered during language training (Tippet et al., 2015). This technology provides a critical opportunity to conduct disease intervention. In this study, we **will test our hypothesis that High-Definition tDCS (HD-tDCS) will improve performance on language tasks by increasing functional connectivity and by regulating abnormal neuronal oscillatory patterns.** The rationale for this project is that a determination of the therapeutic efficacy and the associated neural mechanisms of HD-tDCS in lvPPA is likely to offer a scientific framework whereby new stimulation parameters, conditions, and target sites can be deciphered.

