2.2. Significance

If this mechanistic study succeeds, we will be able to **1)** provide conceptual proof that language performance can be improved by targeting specific dysfunctional neural networks during the clinical phase of disease. **2)** determine whether stimulation intervention reaches specific neural network targets and assess the network level responses; **3)** predict if the network activity modulation can concurrently improve language performance; and **4)** provide essential information needed to prepare future pivotal device trials.

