4. STUDY DESIGN

4.1. Overall Design

This study will test our hypothesis that HD-tDCS will improve performance on language tasks by increasing functional connectivity and by regulating abnormal neuronal oscillatory patterns. The language performance and functional connectivity changes will be determined in a randomized, double-blind, sham-controlled crossover manner, in which a stimulation of up to 2mA in the targeted cortical tissue or sham is administered to 20 IvPPA subjects age 45 years and older. The order of treatments is counterbalanced in a within-subject crossover design, as illustrated in Fig. 2 below. In brief, study participants will receive sham during one treatment period and stimulation during the other treatment period.

Figure 2. Study Design and tDCS Treatment Protocol

The Screening Visit includes medical history, Language Assessment battery, MRI safety screening, and TMS Neuronavigation. Visit 1 (Baseline) will include fMRI and MEG. Additionally at Visit 1, and for 9 additional days in a two-week period (Tx Period 1), each subject will undergo real stimulation or sham and simultaneous word and non-word reading and repetition tasks. At the end of Tx Period 1, a 16-week washout period begins. After the first 8 weeks of the 16-week washout period, subjects return for Assessment Visit 1 where they receive the Language Assessment battery, including the reading and non-word repetition tasks tested at baseline, and 'trained' during each of the stimulation sessions. After the 16-week washout period, Tx Period 2 begins. Subjects undergo stimulation or sham and the simultaneous word and non-word reading and non-word repetition tasks for 10 days over a two-week period. Eight weeks after the end of Tx Period 2, subjects receive the Language Assessment Battery at Assessment Visit 2, which is the last study visit.

An unblinded member of the study team having no contact with the study subjects will randomize them to the treatment conditions, while the language assessment battery of tests will be delivered by a blinded member of the study team. The language training exercises used during each tDCS session as well as the tDCS intervention itself will be delivered by a blinded, qualified and formally tDCS-trained member(s) of the study team.

Data safety is monitored by three data safety monitoring board (DSMB) members who are not related to the study.

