6.7. Expected Results, Deliverable, and Problems

Through this study, we expect to realize two goals: **Scientifically**, we will demonstrate that active HD-tDCS can increase language-network functional connectivity and improve abnormal patterns of resting state neuronal frequencies and synchronizations. **Clinically**, we expect that the changes in network activity after the 2-week stimulation period will lead to language improvement. This study can provide conceptual proof for a rehabilitation intervention. In addition, this study will provide information and address the power of adequate enrollment, protocol adherence, subject retention, and safety for future pilot and pivotal trials.

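### Section 6.5 is headed as a before/after connectivity-language analysis but models only baseline connectivity and omits subject and period terms, so no analysis tests the link between connectivity change and language change

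*Protocol*

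**What the plan says.** The hypothesis is mechanistic. Protocol section 1 says that HD-tDCS "will improve performance on language tasks by increasing functional connectivity and by regulating abnormal neuronal oscillatory patterns", and section 4.1 repeats it. Section 2.2 says that, if the study succeeds, the team will be able to "predict if the network activity modulation can concurrently improve language performance". Section 6.7 adds: "we expect that the changes in network activity after the 2-week stimulation period will lead to language improvement".

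Section 6.5 is the only model containing both the language score (LG) and language-network connectivity (LFC). Its heading is "Prediction of Changes in Correlation Between LFC and LG Before and After tDCS" and its purpose is to "test the difference in slope and intercept between the active stimulation and sham groups". The model is

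LG(s,g) = β0,0 + β0,1·A(s,g) + β1,0·LFC(s) + β1,1·LFC(s)·A(s,g) + Res(s).

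A(s,g) is 1 "If the subject is in the active stimulation group" and 0 in the sham group. LFC(s) "represents baseline LFC for subject s (for simplicity, nuisance regressors are not shown".

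Section 6.2 had given LG and LFC a time index and defined g as two groups of 10, each of which receives both conditions. The section on randomization and dosing confirms that everyone crosses over. Section 5.1 and Table 1 schedule MRI at visits 1, 10, 12 and 21, and the language battery at screening and visits 10, 11, 12, 21 and 22.

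The SAP says that small sample size ruled out group-level analysis. It describes language tests only.

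**The concern.** The heading promises a comparison before and after stimulation, but nothing measured after stimulation enters on the connectivity side. LG has also lost its time index and is not defined as a post-treatment or a change score. A reader who follows section 6.5 exactly gets an answer to a different question from the one it poses.

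The omission matters because this is the only place where the two measures meet. If stimulation improved language and also raised connectivity, the two results would sit side by side, with no analysis of whether the participants whose connectivity rose were those whose language improved. The mechanistic sentence in the hypothesis would then rest on juxtaposition.

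The second matter is the error structure. A crossover gives each participant an active and a sham result, and these are correlated. A model with neither a subject nor a period term does not use that pairing and does not separate treatment from time in a progressive disease.

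**Working it through.** The protocol states no power, sample size or effect size for section 6.5, so there is no figure to reproduce.

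**Step 1. What the coefficients can show.** With LFC(s) fixed at baseline:
- β1,0 is the association of baseline LFC with LG under sham.
- β0,1 is the active-sham difference at LFC = 0 (at mean LFC, if LFC is centred).
- β1,1 is the change in that difference per unit of baseline LFC, which is effect modification.

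No coefficient involves LFC after stimulation or its change. Baseline is also ambiguous, because scans precede both treatment periods (visits 1 and 12).

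**Step 2. Is the link analysed elsewhere?**
- 6.3 analyses LG alone.
- 6.4 analyses LFC alone.
- 6.6 analyses MEG, reusing the fMRI regression models. If that includes 6.5, the same limit carries over.
- The SAP has no connectivity or MEG analysis.

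So the components have planned analyses and the link has none.

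**Step 3. Illustration of step 1.** A crossover of 20 participants (10 per sequence) was simulated, 3000 runs per setting, with assumed residual SD 1, mean gain 0.5, SD of gain 0.5 and within-subject correlation ρ = 0.5, 0.7 and 0.9. Each setting was run with full mediation through connectivity and with none.
- The 6.5 interaction β1,1 averaged between -0.02 and 0.02 in every setting. It was rejected in 4.7 to 5.5% of runs (one row per participant) or 0 to 1.6% (two rows), whether or not mediation was present.
- Regressing the active-minus-sham LG difference on the active-minus-sham difference in LFC change gave a mean slope of 1.00 under full mediation, rejected in 79 to 80%, 94% and over 99% of runs as ρ rose. With no mediation the slope was about 0.00, rejected in 4 to 6%.

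These rates depend on the assumed values. That β1,1 does not respond to mediation follows from step 1.

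**Step 4. Cost of the missing subject term.** Take residual SD σ and residual within-subject correlation ρ, after baseline LFC and the nuisance regressors. The documents do not give ρ, so 0.5, 0.7 and 0.8 are assumed. For the active-sham contrast at mean LFC:
- Correct paired variance with 20 participants: 2σ²(1-ρ)/20.
- Two rows per participant treated as independent: 2σ²/20. SE ratio = √(1/(1-ρ)).
- One row per participant, 10 against 10: 2σ²/10. SE ratio = √(2/(1-ρ)).

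| ρ | Two rows, independent | One row, 10 v 10 |
|---|---|---|
| 0.5 | √2.00 = 1.4 | √4.00 = 2.0 |
| 0.7 | √3.33 = 1.8 | √6.67 = 2.6 |
| 0.8 | √5.00 = 2.2 | √10.0 = 3.2 |

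Under the two-row reading the estimate itself is essentially the paired one, and only its reported SE is wrong. In the simulation with no effect, a nominal 5% test of β0,1 then rejected 0.7% of the time at ρ = 0.5 and 0.1% at ρ = 0.7. Under the one-row reading, half of each participant's treatment information is left out.

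**The case against.** The strongest reply is that this is an ancillary model in a pilot. The primary objective is language efficacy. The three specific aims and the three tiers of outcome cover language, connectivity and MEG, and none is defined as an LFC-LG relation. The sentence in section 2.2 is conditional on success and does not specify an analysis. This stands. A reader might infer that the central hypothesis as a whole goes untested, or that connectivity change is never analysed. The documents do not support either inference, because 6.3, 6.4 and 6.6 plan analyses of the components.

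The second reply is that A(s,g) need not mean parallel groups. Section 6.4 uses group loosely for sham versus stimulation, which suggests a condition indicator with two rows per participant. That is a fair reading, so the text does not establish that crossover participants are compared as independent groups. The subject and period terms are missing either way. Nor does the trial at large give up within-subject precision: 6.3 and 6.4 both carry a random subject factor, and the loss is confined to 6.5.

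Third, ρ should be the correlation remaining after adjustment. If the covariates absorb much of the between-subject variation, it will be lower than the raw correlation and the SE factors will be smaller. This is correct, and is why the factors are shown as a range.

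Fourth, the SAP says that group-level analysis was not possible, so the regression may never have been run. That bears on which remedy is feasible. It does not supply the missing analysis.

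**Conclusion.** The point holds in a limited form. As written, section 6.5 cannot answer the question in its heading. It is a baseline-moderator model, and no part of the protocol or SAP relates change in connectivity to change in language. The claim that improvement comes "by increasing functional connectivity and by regulating abnormal neuronal oscillatory patterns" therefore has component analyses but no analysis of the link. This rests on the text alone.

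The 6.5 equation also omits subject and period terms. The SE of its active-sham contrast exceeds the paired one by a factor of 1.4 to 2.2 (two rows treated as independent) or 2.0 to 3.2 (each participant coded once). These factors rest on assumed ρ of 0.5 to 0.8 and 20 participants in balanced sequences.

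Two further inferences should be resisted. An association between the two changes would be compatible with mediation but would not prove it. The documents give a scan schedule, which does not show that usable paired data exist for all 20 participants.

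**What to change.** - Define, by named visits, the pre-to-post change in LG and in LFC for each participant and period (screening or visit 1 to visit 10; visit 12 to visit 21).
- Regress the active-minus-sham difference in LG change on the active-minus-sham difference in LFC change, with a sequence term to absorb period. With 20 complete participants this leaves 20 - 3 = 17 residual degrees of freedom.
- Alternatively, fit a mixed model for LG change with treatment, period, LFC change and a random subject effect, separating within-subject from between-subject LFC change. The two approaches are related but not identical, so name one in advance.
- Label the analysis exploratory and associational. State whether MEG follows the same form.
- Keep the present model if wanted, retitled as a baseline-LFC moderator analysis, with subject and period terms and an explicit definition of LG(s,g), A(s,g) and baseline.
- If too few participants remain for a group-level model, as the SAP indicates, report paired LFC and LG changes descriptively by participant and period, and state that the connectivity-to-language link was not tested.

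The cost is a change of wording in section 6.5 and the SAP, a little extra analysis and a softer mechanistic claim. The scheduled scans and language tests suffice, so no new procedure is needed.
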